3.2 Allocation to Interventional Group

After completing 4 weeks of BT, subjects will attend a randomization visit (described to subjects as a “progress assessment visit”) at which their weight will be measured, and they will be categorized as an early non-responder (loss of < 2.0% of initial weight) or early responder (loss of ≥ 2.0%). After early non-responders’ eligibility is confirmed via a medical assessment, they will be randomly assigned in a 1:1 ratio, in randomly permuted blocks of 2 to 4 subjects, to one of the two treatment conditions. To maintain investigator blinding, randomization will be carried out by Penn’s Investigational Drug Services who will

purchase phentermine and package the study medications (phentermine or placebo) in blinded capsules. The first subject to meet the randomization criteria will be assigned the first number in the sequence; each subsequent subject to meet randomization criteria will be assigned the next number in the sequence.

3.3 Study Endpoints

3.3.1 Primary Study Endpoints

The primary endpoints of phase 1 are percent weight loss from the start of the BT run-in (week -4) to randomization (week 0), as well as categorization as an early non-responder who lost < 2.0% of initial weight at randomization (co-primary outcomes), as predicted by postprandial satiety ratings (measured by visual analogue scales (VAS) during a test meal), postprandial change in GLP-1, and gastric emptying (measured using an acetaminophen test) at baseline.

The primary endpoint of phase 2 is change in body weight (i.e., % reduction in initial weight), as measured from randomization to week 24.

3.3.2 Secondary Study Endpoints

Secondary endpoints of phase 1 are percent weight loss from the start of the BT run-in (week -4) to randomization (week 0) and categorization as an early non-responder who lost < 2.0% of initial weight at randomization, as predicted by additional behavioral characteristics (hunger as measured by VAS ratings, RRV_{food} as measured using a computer task, and impulsivity as measured using a delay discounting computer task) and neuropeptides (higher fasting ghrelin, lower fasting leptin, and lower postprandial changes in insulin and PYY).

Secondary endpoints of phase 2 will include change in body weight in kg from randomization to week 24, as well as the portion of early non-responders who achieve a post-randomization loss of $\geq 5\%$ and $\geq 10\%$ of initial body weight. We will also examine differences between non-responders treated with BT+M vs. BT+P in changes in hunger, satiety, the reinforcing efficacy of food, and impulsivity (measured as described above) between randomization and week 24. The groups also will be compared on changes in past week VAS ratings of hunger, fullness, food preoccupation, food liking, and cravings as measured at treatment visits. A comparison will also be made in percent weight loss from randomization to week 24 between early non-responders treated with BT+M and early responders treated with BT alone.

3.3.3 Exploratory Endpoints

An exploratory analysis will compare the two randomized groups (BT+M vs. BT+P) on changes from randomization to week 24 in CVD risk factors (i.e., blood pressure, triglycerides, LDL and HDL cholesterol, and waist circumference), glycemic control (i.e., fasting blood sugar), quality of life (as measured by the Short Form Health Survey (SF-36), mood (as measured by the Patient Health Questionnaire (PHQ-9)), and physical activity (Paffenbarger Physical Activity Questionnaire).

An exploratory factor analysis will be used to determine whether primary and secondary predictor variables cluster into phenotypes. Exploratory endpoints will also include additional potential predictors of early response to BT. These will include measures of hunger (i.e., Eating Inventory [EI], past-week visual analogue scale [VAS] ratings), RRV_{food} (i.e., Power of Food Scale [PFS]), the reinforcing efficacy of food, general sensitivity to reward (i.e., the Behavioral Inhibition/Activation Scale [BIS/BAS]), impulsivity (i.e., the Barratt Impulsiveness Scale [BIS-15]), appetite (past-week VAS ratings), cognitive restraint (EI), disinhibition (EI), binge eating (i.e. the Questionnaire on Eating and Weight Patterns [QEWP-5]), food craving (i.e., Food Craving Questionnaire – Trait – reduced [FCQ-Tr]), emotional eating (Dutch Eating Behaviour Questionnaire [DEBQ]), perceived barriers to healthy eating and physical activity, diet and exercise self-efficacy (i.e., Weight Efficacy Life-Style Questionnaire [WEL], SCI Exercise Self Efficacy Scale [ESES]), social support for healthy eating and physical activity (i.e., Ball and Crawford Social Support Scale), hours of sleep per week, mindfulness and acceptance (Philadelphia Mindfulness Questionnaire [PHLMS]), food addiction (Yale Food Addiction Scale [YFAS]), indicators of withdrawal (Highly Processed Food Withdrawal Scale [ProWS]), perceived stress (i.e., Perceived Stress Scale), anxiety (i.e., GAD-7), and mood (i.e., PHQ-9).

4 Study Population and Duration of Participation

4.1 Inclusion Criteria

1. BMI $\geq 31 \text{ kg/m}^2$ (or 28 kg/m^2 with obesity-related comorbidity)
2. Age ≥ 18 years and ≤ 70 years
3. Eligible female patients will be:
 - non-pregnant, evidenced by a negative urine pregnancy test
 - non-lactating
 - surgically sterile or postmenopausal, or they will agree to continue to use an accepted method of birth control during the study. Acceptable methods of birth control are: hormonal contraceptives; double barrier method (condom with spermicide or diaphragm with spermicide); intrauterine device; surgical sterility; abstinence; and/or postmenopausal status (defined as at least 2 years without menses).
4. Subjects must:
 - have a primary care provider (PCP) who is responsible for providing routine care
 - understand and be willing to comply with all study-related procedures and agree to participate in the study by giving written informed consent
 - plan to remain in the Philadelphia area for the next 9 months or more

4.2 Exclusion Criteria

1. Pregnant or nursing, or plans to become pregnant in the next 9 months.
2. Uncontrolled hypertension (systolic blood pressure $\geq 140 \text{ mm Hg}$ or diastolic blood pressure $\geq 90 \text{ mm Hg}$)
3. Type 1 diabetes
4. Type 2 diabetes
5. A fasting blood glucose $>126 \text{ mg/dL}$ (on second assessment after first elevated value, patients are excluded if they have both fasting blood glucose $> 126 \text{ mg/dL}$ and HbA1c ≥ 6.5)
6. History of cardiovascular disease (e.g., coronary artery disease, stroke, arrhythmias, congestive heart failure, or heart block greater than first degree)
7. Clinically significant hepatic or renal disease
8. Hyperthyroidism
9. Other thyroid disease, not controlled.
10. History of malignancy (except for non-melanoma skin cancer) in past 5 years
11. Narrow angle glaucoma
12. Presence or history of marked agitation
13. Current severe major depressive episode (BDI-II score ≥ 29), current active suicidal ideation, or history of suicide attempts within the past 5 years.
14. Any severity of thought or bipolar disorder, or bulimia nervosa.
15. Psychiatric hospitalization within the past 6 months
16. Self-reported alcohol or substance abuse within the past 6 months, including at-risk drinking (current consumption of ≥ 14 alcoholic drinks per week)
17. Past year history of drug abuse.
18. Use in the past 2 weeks of monoamine oxidase inhibitors.
19. Current use of serotonin-norepinephrine reuptake inhibitors (SNRIs; e.g., venlafaxine, duloxetine, desvenlafaxine, milnacipran, levomilnacipran).
20. Use in past 6 months of medications known to induce significant weight loss (i.e., prescription weight loss medications) or weight gain (e.g., chronic use of oral steroids, second generation antipsychotics)
21. Loss of $\geq 5\%$ of initial body weight within the past 6 months
22. History of (or plans for) bariatric surgery (e.g., roux en y gastric bypass, sleeve gastrectomy, gastric banding), endoscopic intragastric balloon, or aspire assist.

23. Inability to walk 5 blocks comfortably or engage in some other form of aerobic activity (e.g., swimming)
24. Known or suspected allergy to sympathomimetic amines or related products
25. The receipt of any investigational drug within 6 months prior to this trial
26. Previous participation in this trial (e.g., randomized and failed to participate)
27. Changes to any chronic medication (type or dosage) within the past 3 months.
28. Any serious or unstable medical or psychological condition that, in the opinion of the investigator, would compromise the patient's safety or successful participation in the study

Other Therapy: Subjects will be expected to use medications (prescribed by their PCP) to control traditional cardiometabolic risk factors (e.g., hypertension, hypercholesterolemia, etc) and other co-morbid conditions, with the exception of medications listed above under "exclusions." In all cases, the subjects' PCP will be asked at the study's outset to keep medication doses constant throughout the study, whenever possible. Subjects will be expected to have been on their medication regimen (including the dose) for 3 months prior to beginning the BT program.

4.3 Randomization Criteria

To be eligible to participate in the randomized phase of the trial, subjects must also:

1. Complete at least 3 out of 4 treatment sessions during the 4-week BT run-in and attend a randomization visit. Attending an in-person makeup session within one week of a missed visit will count as having attended the run-in visit.
2. Lose < 2.0% of initial weight during the 4-week BT run-in.

Subjects who complete at least 3 out of 4 treatment sessions during the 4-week BT run-in and have lost \geq 2% of initial weight at the randomization visit will be provided with 24 weeks of BT during phase 2 of the study, but will not be eligible for randomization to a study medication.

4.4 Subject Recruitment

Subjects will be recruited from the greater Philadelphia area via flyers and online, radio, and print advertisements, through referrals from Penn primary care practices, and through Penn's iConnect system. All recruiting materials used in the study will have IRB approval.

4.5 Duration of Study Participation

The total duration of the study subjects' participation is expected to be 8 months. This includes a screening visit, baseline visit, 28 total weeks of BT (4 weeks before and 24 weeks after the randomization visit), and a post-treatment assessment.

4.6 Total Number of Subjects and Sites

Recruitment will end when 150 subjects are enrolled. It is expected that approximately 50 of these subjects (33%) will become classified as early non-responders to BT and enrolled in the randomized trial.

4.7 Vulnerable Populations:

Children, pregnant women, fetuses, neonates, or prisoners are not included in this research study.

5 Study Interventions

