- Phase 2: To test the effect of augmenting BT with the weight loss medication phentermine 15.0 mg (BT+M), compared to BT plus placebo (BT+P), on weight loss in early non-responders who lose < 2.0% of initial weight during a 4-week behavioral run-in. Percent weight loss from randomization to week 24 is the study's primary endpoint.

Secondary:

- Phase 1: To examine whether additional behavioral characteristics (higher fasting hunger, relative reinforcing value of food [RRV_{food}], and impulsivity) and neuropeptides (higher fasting ghrelin, lower fasting leptin, and lower postprandial changes in cholecystokinin and peptide YY) predict 4-week weight loss, as well as categorization as a non-responder during the BT run-in.
- To compare the portion of early non-responders who achieve a post-randomization loss of $\geq 5\%$ and $\geq 10\%$ of initial body weight with BT+M and BT+P.
- To compare non-responders treated with BT+M vs. BT+P in changes in hunger, satiety, RRV_{food}, and impulsivity between randomization and week 24.
- To explore differences in percent weight loss from randomization to week 24 between early non-responders treated with BT+M and early responders treated with BT alone.

Number of Subjects

150 subjects (180 in-person screenings to obtain 150)
60 subjects randomized to study medication(s)

**Main Inclusion and
Exclusion Criteria**

Key Inclusion Criteria

1. BMI $\geq 31 \text{ kg/m}^2$ (or 28 kg/m^2 with obesity-related comorbidity)
2. Age ≥ 21 years and ≤ 70 years
3. Has a primary care provider (PCP) responsible for providing routine care
4. Plans to remain in the Philadelphia area for the next 9 months or more

Key Exclusion Criteria

5. Pregnant or nursing, or plans to become pregnant in the next 9 months.
6. Uncontrolled hypertension (systolic blood pressure $\geq 140 \text{ mm Hg}$ or diastolic blood pressure $\geq 90 \text{ mm Hg}$)
7. Type 1 diabetes
8. Type 2 diabetes
9. A fasting blood glucose $> 126 \text{ mg/dL}$ (on second assessment after first elevated value, patients are excluded if they have both fasting blood glucose $> 126 \text{ mg/dL}$ and HbA1c ≥ 6.5)
10. History of cardiovascular disease (e.g., coronary artery disease, stroke, arrhythmias, congestive heart failure, or heart block greater than first degree)
11. Clinically significant hepatic or renal disease
12. Hyperthyroidism
13. Other thyroid disease, not controlled.
14. History of malignancy (except for non-melanoma skin cancer) in past 5 years

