3.1 General Design

This is a two-phase study. Phase 1 will evaluate obesity-related behavioral and biological characteristics as potential mechanisms of non-response to BT. Phase 2 is a double-blind, placebo-controlled, RCT to test whether augmenting BT with weight loss medication improves 24-week weight loss, as compared to BT with placebo, in subjects identified as early non-responders to 4 weeks of individual behavioral weight control. Subjects will be a total of 150 adults, aged 21-70 years, with a body mass index (BMI) of 31 kg/m² or above (28 kg/m² with an obesity-related comorbidity). Subjects will attend a screening visit in which they will complete a behavioral evaluation with a psychologist and a medical history. In phase 1, eligible subjects will complete questionnaires and an in-person baseline assessment of obesity-related behavioral characteristics (satiety, hunger, RRV_{food}, and impulsivity), neuropeptides, and gastric emptying. Within 2 weeks of this assessment, they will begin an initial 4-week BT “run-in” delivered individually in 20-30 minute sessions. The primary goal of phase 1 will be to evaluate baseline postprandial satiety, postprandial change in GLP-1, and gastric emptying as predictors of early weight loss after 4 weeks of BT. We will also examine whether these variables predict categorization as an early non-responder to BT who loses < 2.0% of initial weight (vs. early responders who lose ≥ 2.0%; approximately 33% vs. 66% of the sample, respectively).

In phase 2, early non-responders (who lost < 2.0% during the BT run-in) will be randomly assigned to 24 weeks of: 1) BT plus placebo (BT+P); or 2) BT plus medication (BT+M; phentermine 15.0 mg). Both treatment groups will continue to attend 20-30 minute individual BT sessions, weekly for the first 12 weeks and every other week for the last 12 weeks (total of 18 visits). Both treatment groups will also take once daily study medication (placebo or phentermine 15.0 mg) for the duration of the intervention period (with titration between randomization and week 2). Early BT responders identified during the run-in will receive the same 24-week BT program, but will not receive study medication or be included in the randomized trial. The assessments administered at baseline – questionnaires, including behavioral testing, blood draws, and measurements of body weight – will be repeated at randomization (week 0) and at week 24.

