5.2 BT Intervention

Following randomization, all subjects will continue to attend individual (20-30 minute) BT sessions weekly for 12 weeks, then every other week until week 24 (total of 18 sessions). Subjects will be instructed to continue to follow their calorie goal and to engage in low-to-moderate intensity physical activity (e.g., walking), gradually building to a goal of ≥ 180 minutes per week (spread across 5 days) by week 24. They will be provided a curriculum on behavioral weight control, based on prior studies,^{80, 81} that includes self-monitoring, stimulus control, goal-setting, problem-solving, cognitive restructuring, and relapse prevention. Subjects will continue to monitor their food intake, physical activity, and weight online (e.g., Myfitnesspal) unless they prefer paper diaries. Subjects who miss a treatment visit will be contacted by the research coordinator and invited to complete a make-up session with study staff.

Initially, BT sessions were primarily provided in-person (make-up sessions were conducted in person or by phone). Consistent with University policy, all BT sessions will be provided by telehealth (phone or secure teleconferencing system) while recommendations to maintain remote activities due to COVID-19 remain in place.

BT interventionists will include RDs, NPs, and psychologists who are experienced in delivering lifestyle modification. Before beginning the study, interventionists will receive a 2-hour overview of obesity and its behavioral management, followed by ongoing weekly group clinical supervision. The PI will observe each provider delivering a treatment session at least once every 6 months to provide individualized feedback and ensure protocol adherence.

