Phase 2: For the primary outcome - percent weight change from randomization to week 24 among early non-responders - estimated group means, variances, and attrition rates were derived from data from prior studies conducted at our Center and from previous research in early non-response to BT e.g.,⁴. The estimated treatment effect is based on the placebo-subtracted effect of 28 weeks of phentermine 15.0 mg of 4.5 kg (4.4% of initial weight), as determined by a multi-arm RCT that enrolled 219 total patients in the placebo and phentermine 15.0 mg groups.⁷⁷ We selected this result as the basis of our power analysis because it most closely matched the phentermine dose and duration used in the present study. Other previous RCTs examining the effect of phentermine monotherapy have typically administered a 30.0 mg dose for 12 to 16 weeks. The majority of these trials have achieved larger placebo-subtracted weight losses of 5.4 to 7.8 kg.^{72, 74-76} (One randomized trial reported a 4.0 kg placebo-subtracted loss with a different formulation, phentermine resin 30.0 mg,⁷³ and one reported a 3.3% placebo-subtracted loss when both phentermine 37.5 mg and placebo were combined with a 900-1100 kcal/day meal replacement diet, resulting in large mean weight losses in both groups.¹⁰⁹) An additional study suggested that the difference in mean weight loss between phentermine 15.0 mg and phentermine 30.0 mg (both when combined with lorcaserin) is small (0.6 kg mean difference).¹¹⁰ We therefore believe that participants provided with 24 weeks of phentermine 15.0 mg are likely to achieve a placebo subtracted loss of $\geq 4.5\%$ of initial weight. (Most early phentermine studies reported results in kg, which is roughly equivalent to percent weight loss in populations with obesity.)

We predict a 24-week post-randomization weight loss among early non-responders of 6.5% in BT+M and 2.0% in BT+P, with expected standard deviations of 5.5%. We expect 33% of the initial baseline sample of 150 subjects to be categorized as early non-responders following the BT run-in.^{4, 7, 8} Based on these estimates, a randomized sample size of 50 non-responders (25 per group), assuming a 20% attrition rate, will give us 81.5% power to detect between-treatment group differences at week 24 of 4.5% (effect size: $d = 0.82$).

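### The plan gives two randomised numbers (60 and about 50), and the stated 81.5% Phase 2 power holds at neither under the planned two-tailed test with 20% attrition

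*Combined protocol and SAP*

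**What the plan says.** **Number randomised.** The Study Summary, under Number of Subjects, gives 60 ("60 subjects randomized to study medication(s"). Section 4.6 stops recruitment at 150 enrolled and states: "It is expected that approximately 50 of these subjects (33%) will become classified as early non-responders to BT and enrolled in the randomized trial". The comment in 3.1 aims for at least 50 early non-responders from 150. Section 3.1 also gives the expected split between non-responders and responders as "approximately 33% vs. 66% of the sample, respectively".

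**Power.** Section 9.1 says that "a randomized sample size of 50 non-responders (25 per group), assuming a 20% attrition rate, will give us 81.5% power" to detect a 4.5-point difference at week 24, from mean losses of 6.5% and 2.0% with an SD of 5.5% (d = 0.82). It gives alpha as .05 without stating sidedness, and claims at least 80% power for all three primary outcomes. Section 9.2 makes the analyses two-tailed at 0.05.

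**Steps between enrolment and randomisation.** Section 4.3 requires subjects to "Complete at least 3 out of 4 treatment sessions during the 4-week BT run-in and attend a randomization visit". Section 7.5 ends participation for anyone who has no randomisation visit within 2 weeks of the end of the run-in. Section 7.1 requires an EKG before entry to the randomised trial. Section 7.2 requires willingness, an eligibility check and a pregnancy test.

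**Make-up sessions.** Section 4.3 says: "Attending an in-person makeup session within one week of a missed visit will count as having attended the run-in visit". Section 5.2 says that, while COVID-19 recommendations for remote activity remain, "all BT sessions will be provided by telehealth". Section 7.5 allows make-up sessions in person or by phone, except at visits where medication is handed out.

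**The concern.** The randomised number and its power are the figures on which the Phase 2 primary comparison is judged. Two targets stand in current text, and the lower one is simply the expected non-response rate applied to everyone enrolled. The power figure attached to it looks too high for 20 completers per arm and a two-tailed test. If it is left, a null week-24 result could be read as coming from a trial with more than 80% power, when its planned test has about 71%. The Safety Monitoring Committee, which reviews enrolment against the protocol, would also have no single number to check the randomised trial against.

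**Working it through.** **Inputs.** 150 enrolled (4.6); 33% non-response (4.6, 9.1); 60 randomised (Summary) or 50 (9.1); 1:1 allocation (3.2); 20% attrition, difference 4.5 points, SD 5.5 (9.1); two-tailed 0.05 (9.2).

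**Yield.** 150 × 0.33 = 49.5, which reproduces the 50. For the Summary's figure, 60/150 = 40% non-response with nobody lost. If the true rate is 33% and nobody is lost, the binomial chance of at least 60 non-responders is about 4%.

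**Power.** d = 4.5/5.5 = 0.818. With m completers per arm, the two-sample t-test has df = 2m − 2 and noncentrality d × √(m/2). Power is the probability that the noncentral t passes the critical value.

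Reproducing the stated 81.5% first:

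| Reading | m per arm | Noncentrality | Critical t | Power |
|---|---|---|---|---|
| 50 randomised, 20% attrition, one-sided | 25 × 0.8 = 20 | 2.587 | 1.686 | 81.5% |
| 50 randomised, no attrition, two-sided | 25 | 2.893 | 2.011 | 80.9% |
| 50 randomised, 20% attrition, two-sided | 20 | 2.587 | 2.024 | 71.3% |

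The first row matches exactly. The second comes close (81.1% if d is rounded to 0.82). The third combines the attrition stated in 9.1 with the test stated in 9.2, and it does not match.

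At the Summary's number, 60 randomised gives 30 × 0.8 = 24 completers per arm, noncentrality 2.834, critical t 2.013 and two-sided power 79.2%.

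**Margin before randomisation.** The 20% attrition in 9.1 is applied to the randomised sample. No rate is given for loss between enrolment and randomisation, so the losses below are assumptions and not estimates. They are applied to 49.5 non-responders, followed by 20% attrition:

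| Assumed loss | Randomised | Completers per arm | Two-sided power |
|---|---|---|---|
| 5% | 49.5 × 0.95 = 47.0 | 18.8 | about 68% |
| 10% | 49.5 × 0.90 = 44.6 | 17.8 | about 66% |
| 15% | 49.5 × 0.85 = 42.1 | 16.8 | about 63% |
| 20% | 49.5 × 0.80 = 39.6 | 15.8 | about 61% |

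**Make-up wording.** Read literally, 4.3 credits only an in-person make-up toward the 3-of-4 rule. Under 5.2 every session may be remote, and 7.5 accepts phone make-ups. The three sections do not say whether a remote make-up counts toward eligibility for randomisation.

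**The case against.** - **The 50 can still be reached with some loss.** A reader might infer that 50 is attainable only if nobody is lost, or that fewer than 50 will be randomised. The documents do not support this. The 50 and the 33% are both described as approximate. A rate of about 35% with 5% loss, or 37% with 10% loss, still gives 50. Classification takes place at the randomisation visit (3.2), so the 33% could already be net of non-attendance. Most exclusions relevant to the drug are applied at entry, and consent at screening already covers possible assignment to medication or placebo (13.4). What stands is narrower: at the planned rate there is no stated margin, and the size of any shortfall is unknown.
- **Run-in loss is not the main cause of the power gap.** This is correct. With all 50 randomised, two-sided power is already 71.3%, so the gap comes from sidedness or from how attrition was handled. The 60 would raise power, not lower it.
- **A one-sided calculation is not proven.** Section 9.1 is silent on sidedness, and the two-sided value without attrition is within a point. Either way, the figure does not describe the planned test with the stated attrition.
- **The mixed model may gain precision over a completer t-test.** Possibly, but 8.1 limits primary-outcome weights to baseline, randomisation and week 24, and no correlation is given. If the gain is represented as variance explained by a covariate, a correlation of about 0.45 would be needed to reach 80% at 20 per arm (80.6%; 78.6% at 0.40).
- **The make-up wording may affect few people.** A reader might infer that it removes a countable number of subjects. It touches only those who miss at least two sessions, the remote period is temporary, and nothing in the documents allows a count.
- **The research is described as preliminary, and 3.1 openly explains the limit on sample size.** This is a good reason not to ask for more subjects. It does not excuse a power figure that the planned test does not give.

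**Conclusion.** The point holds in this form. Two randomised numbers stand unreconciled, and the 60 is not supported by the plan's own 33%. The Phase 2 power is overstated by about 10 points at 50 randomised (81.5% stated, 71.3% computed). It remains just under 80% at 60 (79.2%). These results rest on the plan's effect size, SD and attrition, its two-tailed 0.05 test, and a completer t-test as the approximation to the mixed model. The figures of 47 to 40 randomised and 68 to 61% power depend on assumed losses of 5 to 20%; they show how sensitive the plan is and do not predict a shortfall. The make-up wording is a separate inconsistency of unknown effect.

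**What to change.** 1. State one randomised number in the Summary, 3.1, 4.6 and 9.1, and correct or explain the 60.
2. In 9.1, restate Phase 2 power for that number as two-sided at 0.05 with 20% attrition (71.3% at 50; 79.2% at 60), and amend the claim of at least 80% power for all three primary outcomes. If a precision gain from the mixed model is claimed, state the correlation assumed.
3. In 4.6 and 9.1, give the expected loss between enrolment and randomisation as a labelled assumption with a range, and show the randomised number and power that follow.
4. Reconcile the make-up session wording in 4.3 with 5.2 and 7.5. Which rule applies is for the investigators to decide.

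The cost is corrected text in a few sections and a less favourable stated power. No added enrolment and no change of design is asked for.
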